7.3.2. Summary Measure

Time to Next Treatment

If there are sufficient number of responders who started new anti-cancer treatment due to any reasons by dose level, time to next treatment will be summarized descriptively using median(s) and quartiles.

Rate of VGPR or Better

The number and percentage of participants with the BOR in the following response categories will be summarized: sCR, CR, and VGPR. The corresponding exact 95% CI for rate of VGPR or better will also be provided. Participants with unknown or missing responses will be treated as non-responders, i.e., these participants will be included in the denominator when calculating percentages of response.

7.3.3. Population of Interest

Time to next treatment and rate of VGPR or better analyses will be based on the All Treated population, unless otherwise specified.

8. SAFETY ANALYSES

The safety analyses will be based on the All Treated population, unless otherwise specified.

8.1. Adverse Events Analyses

Adverse events analyses including the analysis of adverse events (AEs), Serious (SAEs), ir (immune-related) AEs associated with pembrolizumab, and other significant AEs and serious and other significant irAEs will be based on GSK Core Data Standards. Details on treatment emergent AEs are provided in Section 16.4.1.2. Dose modifications (dose interruptions, dose reduction, and dose delays) and dose limiting toxicity (DLT) will also be summarized and listed according to GSK Oncology Data Standards. The details of the planned displays are provided in [Appendix 11: List of Data Displays](#).

A summary of non-serious adverse events that occurred in strictly 5% of the subjects or above will be provided (no rounding for the percentage will be used in terms of 5% threshold, e.g., event with 4.99% incidence rate should not be included in this Table). The summary will be displayed by SOC and PT.

Adverse events (AEs) and immune-related adverse events (irAEs) will be graded by the investigator according to the National Cancer Institute-Common Terminology Criteria for Adverse Events (NCI-CTCAE), Version 4.03 [[NCI](#), 2010]. Adverse events will be coded using the Medical Dictionary for Regulatory Affairs (MedDRA dictionary) and grouped by system organ class (SOC). Immune-related adverse events will be coded using the Medical Dictionary for Regulatory Affairs (MedDRA dictionary) and grouped by preferred terms (PT). In addition, corneal findings will also be graded using the GSK scale for corneal events.

A summary of number and percentage of subjects with any adverse events and immune-related adverse events by maximum grade will be produced. AEs and irAEs will be sorted by Preferred term (PT) in descending order of total incidence. The summary will use the following algorithms for counting the subject (this applies also for subjects with irAEs):

- **Preferred term row:** Subjects experiencing the same AE preferred term several times with different grades will only be counted once with the maximum grade.
- **Any event row:** Each subject with at least one adverse event will be counted only once at the maximum grade no matter how many events they have.

In addition, the frequency and percentage of AEs (all grades) and irAEs (all grades) will be summarized and displayed in two ways: 1) in descending order of total incidence by PT only and 2) in descending order of total incidence by System Organ Classes (SOC) and PT and Maximum Grade for AEs and irAEs. In the SOC row, the number of subjects with multiple events under the same system organ class will be counted once. Otherwise, if AEs and irAEs are not listed in the NCI-CTCAE (version 4.03, [[NCI](#), 2010]), then the AEs and irAEs will be summarized by maximum intensity.

A separate summary will be provided for study treatment-related AEs. A study treatment-related AE is defined as an AE for which the investigator classifies the relationship to study treatment as “Yes”. A worst-case scenario approach will be taken to handle missing relatedness data, i.e. the summary Table will include events with the relationship to study treatment as ‘Yes’ or missing. The summary Table will be displayed in descending order of total incidence by SOC and PT and Maximum Grade for AEs.

All AEs and irAEs will be listed. Additionally, a listing of subject IDs for each individual AE and a listing of subject IDs for each individual irAE will be produced.

A summary of the number of patients experiencing DLTs will be provided. Grade 3 or above corneal events based on the GSK scale for corneal events associated with belantamab mafodotin should be used for evaluation of DLT.

8.2. Adverse Events of Special Interest Analyses

Characteristics (e.g. number of occurrences, action taken, grade, etc) of the following AEs of special interest and identified risk for belantamab mafodotin and AEs of special interest for pembrolizumab will be summarized separately:

- **Belantamab Mafodotin (AESIs)**
 - Corneal events (GSK Scale)
 - Eye Disorders (CTCAE)
 - Thrombocytopenia
 - Infusion related reactions
- **Belantamab Mafodotin (Identified Risk)**
 - Neutropenia
- **Pembrolizumab (AESIs)**
 - Overdose

8.2.1. Belantamab Mafodotin

8.2.1.1. Eye Disorders, Thrombocytopenia, and Infusion Related Reactions

The severity of all AESI will be graded utilizing the National Cancer Institute Common Toxicity Criteria for Adverse Events (NCI-CTCAE) v.4.03 [NCI, 2010]. For thrombocytopenia, in addition to events identified and collected in eCRF, a comprehensive list of MedDRA terms based on clinical review will be used to identify each type of event. Changes to the MedDRA dictionary may occur between the start of the study and the time of reporting and/or emerging data from on-going studies may highlight additional adverse events of special interest, therefore the list of terms to be used for each event of interest and the specific events of interest will be based on the safety review team (SRT) agreements in place at the time of reporting. For infusion related reactions (IRR), events are only considered IRR if the preferred term = “Infusion related reaction” or event was reported on an infusion day after the start of infusion or within 24 hours following end of infusion and led to a temporary interruption or prolongation of infusion time or treatment withdrawal. For keratopathy events (CTCAE) under eye disorders, events are considered keratopathy events if the synonym =

“keratopathy/keratitis”. The details of the planned displays are provided in [Appendix 11: List of Data Displays](#).

Summaries of the number and percentage of subjects with these events will be provided for each type of events separately by preferred term and maximum grade. The time of onset and duration of first occurrence of each type of events will be summarized using summary statistics mean, standard deviation, median, minimum value, and maximum. The number and percentage of subjects who have time of onset of first occurrence and the number and percentage of subjects who have duration of first occurrence will be reported in the following:

Thrombocytopenia and Eye Disorders:

- Time of first occurrence: 1-21, 22-42, 43-63, >63 days
- Duration of first occurrence: 1-21, 22-42, >42 days

Infusion Related Reactions:

- Time of first occurrence: 0-6, >6-12, >12-18, >18-24 hours
- Duration of first occurrence: 0-12, >12-24, >24 hours

The summary of event characteristics will also be provided, including number of subjects with any event, number of events, number of subjects with any event that is serious, number of subjects with any event that is related to study treatment, number of occurrences (One, Two, Three or more), maximum grade and the action taken for the event. Distinct occurrences require at least one day (or hour for IRR) gap between the resolution of all events from first course to the onset of second course. Overlapping occurrences of events are treated as the same occurrence. The percentage will be calculated in two ways, one with number of subjects with event as the denominator and the other with total number of subjects as the denominator. The worst-case approach will be applied at subject level for the maximum grade, i.e. a subject will only be counted once as the worst case from all the events experienced by the subject. For action taken to an event, subject will be counted once under each action, e.g. if a subject has an event leading to both study treatment discontinuation and dose reduction, the subject will be counted once under both actions.

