16.6.4. Safety

Adverse Events
AE'S of Special Interest (belantamab mafodotin)

 Corneal events (GSK Scale): collected in eCRF Eye Disorders (CTCAE) Thrombocytopenia Infusion related reactions
AE'S of Special Interest (pembrolizumab)

 Overdose

Duration of AE

 Calculated as the number of days from AE Start Date to AE Stop Date: 
 AE Start Date = Missing → Elapse Time = Missing AE Stop Date = Missing → Elapse Time = Missing Otherwise → Elapsed Time = AE Stop Date – AE Start Date + 1
ECHO/MUGA

 Change from Baseline for cardiac data, e.g., Left Ventricular Ejection Fraction (LVEF), will be calculated based on the same modality (ECHO or MUGA) throughout the study for each subject. Post-baseline assessments with a different cardiac scan modality will not be used to calculate change from Baseline.

DLT
DLT Evaluable

 Participant is considered DLT evaluable if they fulfilled the 'All Treated' population criteria during part 1 (Dose Escalation) and are followed up for a 21-day period or withdrawn within 21 days due to an AE meeting the definition of a DLT as defined in Section 4.2.3.1 of protocol.

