3.0029	All Treated	See programming notes	Summary of Keratopathy Events (CTCAE) Characteristics II	Report for: Part 1, Part 2, and combined Part 1 and Part 2; Summarize by: dose level (Refer to Section 5.1 for ordering of dose level and omit 1.92 mg/kg if data is not available), Total; Refer to mid205678 (primary_01) Table 3.0200 for guidance.	P-SAC [3], F-SAC [4]
3.0030	All Treated	ESI2a	Summary of Onset and Duration of the First Occurrence of Grade 2 or Above Corneal Events (GSK scale)	Report for: Part 1, Part 2, and combined Part 1 and Part 2; Summarize by: dose level (Refer to Section 5.1 for ordering of dose level and omit 1.92 mg/kg if data is not available), Total; Time of onset: 1-21, 22-42, 43-63, >63. Duration till resolution: 1-21, 22-42, >42.	P-SAC [3], F-SAC [4]
3.0031	All Treated	ESI2a	Summary of Onset and Duration of the First Occurrence of Eye Disorders (CTCAE)	Report for: Part 1, Part 2, and combined Part 1 and Part 2; Summarize by: dose level (Refer to Section 5.1 for ordering of dose level and omit 1.92 mg/kg if data is not available), Total; Time of onset: 1-21, 22-42, 43-63, >63. Duration till resolution: 1-21, 22-42, >42.	P-SAC [3], F-SAC [4]
3.0032	All Treated	ESI2a	Summary of Onset and Duration of the First Occurrence of Thrombocytopenia	Report for: Part 1, Part 2, and combined Part 1 and Part 2; Summarize by: dose level (Refer to Section 5.1 for ordering of dose level and omit 1.92 mg/kg if data is not available), Total; Time of onset: 1-21, 22-42, 43-63, >63. Duration till resolution: 1-21, 22-42, >42.	P-SAC [3], F-SAC [4]

Safety: Tables					
No.	Population	IDSL / Example Shell	Title	Programming Notes	Deliverable [Priority]
3.0033	All Treated	ESI2a	Summary of Onset and Duration of the First Occurrence of Infusion Related Reactions	Report for: Part 1, Part 2, and combined Part 1 and Part 2; Summarize by: dose level (Refer to Section 5.1 for ordering of dose level and omit 1.92 mg/kg if data is not available), Total; Time of onset: 1-21, 22-42, 43-63, >63. Duration till resolution: 1-21, 22-42, >42.	P-SAC [3], F-SAC [4]
3.0034	All Treated	See programming notes	Summary of Corneal Events (GSK scale) by Grade and Visit	Report for: Part 1, Part 2, and combined Part 1 and Part 2; Summarize by: dose level (Refer to Section 5.1 for ordering of dose level and omit 1.92 mg/kg if data is not available) Total. Include Worst-case baseline visit.; Refer to mid205678 (primary_01) Table 3.0340 for guidance.	P-SAC [3], F-SAC [4]

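### The Table 3.0033 categories for infusion-related reactions contradict the hour categories prespecified in SAP Section 8.2.1.1

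*SAP*

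**What the plan says.** SAP Section 8.2.1.1 treats IRRs separately from the other events of special interest. For IRR onset it sets "Time of first occurrence: 0-6, >6-12, >12-18, >18-24 hours", and for IRR duration "Duration of first occurrence: 0-12, >12-24, >24 hours". For thrombocytopenia and eye disorders the same section uses three-week bands, for example "Duration of first occurrence: 1-21, 22-42, >42 days". It also plans mean, SD, median and range for onset and duration of each event type.

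The hour scale appears again in that section's rule for counting occurrences: "Distinct occurrences require at least one day (or hour for IRR) gap".

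The display list in Section 16.11.7 contains one onset-and-duration table for IRRs, Table 3.0033, entitled "Summary of Onset and Duration of the First Occurrence of Infusion Related Reactions". It is due at both the primary and the final analysis. Its programming note reads "Time of onset: 1-21, 22-42, 43-63, >63. Duration till resolution: 1-21, 22-42, >42", with no unit. The notes for Tables 3.0030 (corneal events), 3.0031 (eye disorders) and 3.0032 (thrombocytopenia) give the same cut-points.

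The only duration derivation for adverse events, in Section 16.6.4, works in whole days: "Elapsed Time = AE Stop Date – AE Start Date + 1".

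**The concern.** The body text and the display list give two different specifications for the same table. IRR is a listed event of special interest for belantamab mafodotin, and Section 8.2.1.1 set its bands in hours so that the report can show how soon after infusion a reaction begins and how long it lasts. The Table 3.0033 note looks carried over from the neighbouring rows. If it is programmed as printed, the categorical rows will not show what Section 8.2.1.1 prespecifies, and a reader who compares the table with the plan will find that they do not match.

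**Working it through.** The SAP gives no numerical result to reproduce here. The check is to map the prespecified bands onto the printed ones, under both possible units.

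**Inputs.** Hour bands and the IRR definition: Section 8.2.1.1. Printed bands: Table 3.0033 note, Section 16.11.7. Whole-day duration rule: Section 16.6.4. Study day counted from first dose: Section 16.6.1. 21-day cycles: Section 2.3. Dosing window of ±3 days: Section 6.4.1.

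**Duration, printed bands read as days.** Let s be the clock hour at which the IRR starts (0 to 23) and L its length in hours. The stop date minus start date plus 1 rule gives

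D = floor((s + L)/24) + 1.

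- For L up to 24 hours, s + L is at most 23 + 24 = 47, so D is 1 or 2. Both the 0-12 and the >12-24 hour bands fall wholly in 1-21.
- To leave 1-21, D must reach 22, so s + L must be at least 21 × 24 = 504, that is L ≥ 504 − s. The earliest case is s = 23, giving L = 481 hours (481/24 ≈ 20 days). With s = 0 it is 504 hours (21 days).
- The >24 hour band therefore also falls in 1-21 until the event has lasted about 20 days.

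**Onset, printed bands read as days from first dose.** Section 8.2.1.1 states no origin, so counting from first dose is an assumption. Undelayed infusions fall on day 21(c − 1) + 1 for cycle c. Take an onset on the infusion day or the next:

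| Cycle | Infusion day | Onset day | Printed band |
|---|---|---|---|
| 1 | 1 | 1-2 | 1-21 |
| 2 | 22 | 22-23 | 22-42 |
| 3 | 43 | 43-44 | 43-63 |
| 4 | 64 | 64-65 | >63 |

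The rows would show roughly the cycle of the first IRR. The match is only rough: a Cycle 2 infusion given up to 3 days early falls on days 19 to 21 (22 − 3 = 19), and delays shift later cycles upward. Hours after infusion would not be visible in these categories.

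**Printed bands read as hours.**

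| Prespecified onset band | Where it falls in Table 3.0033 |
|---|---|
| 0-6 h | below 1 h: no category; from 1 h: 1-21 |
| >6-12 h | 1-21 |
| >12-18 h | 1-21 |
| >18-24 h | up to 21 h: 1-21; between 21 and 22 h: no category; from 22 h: 22-42 |

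The same boundaries apply to duration: from 1 h upward, the 0-12 hour band and most of the >12-24 hour band share 1-21. The note contradicts Section 8.2.1.1 under either unit.

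**Whether the hour bands themselves are complete.** An event counts as an IRR if it carries the IRR preferred term, for which no time limit is stated. It also counts if it was reported on an infusion day after the infusion started, or "within 24 hours following end of infusion and led to a temporary interruption or prolongation of infusion time or treatment withdrawal". The second route runs to 24 hours after the end of infusion, so onset measured from the start can exceed 24 hours. The onset bands in Section 8.2.1.1 stop at 24 hours and have no category for such events.

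**The case against.** The strongest reply is that this is an editorial slip with limited consequence. The continuous statistics planned in Section 8.2.1.1 do not depend on the bins. IRR characteristics, preferred terms with maximum grade, and the individual events are covered by Tables 3.0028 and 3.0037 and Listing 1.0028. The table prints no unit, the mock shells were removed for disclosure, and the SAP states no rule that the display list overrides the body text.

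Most of that stands, and it rules out several stronger readings.

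- A reader might infer that the duration summary carries no information. It does not follow: the continuous statistics remain, although they would be coarse if taken from whole days, and an IRR of about three weeks or more would still be separated.
- A reader might infer that the onset bins are equally empty. On a day scale they would show roughly the cycle of first occurrence, which is a different quantity but not a void one.
- A reader might infer that all IRRs lie within 24 hours of infusion. The window belongs only to the route that does not use the preferred term, and neither route caps duration.
- A reader might put nearly all durations in 1-21. That is likely if IRRs last hours, but the SAP gives no IRR duration data, so it is an assumption.

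The contradiction between the two specifications survives. Reading the unlabelled bins as hours does not remove it, and the absence of a precedence rule leaves the programmer without a way to resolve it.

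**Conclusion.** The point holds as an internal contradiction. The Table 3.0033 categories do not implement the hour categories of Section 8.2.1.1. On the day reading, the two shorter duration bands, and the longest one up to about 20 days, fall into a single category, and onset is measured as approximate cycle instead of time since infusion.

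That the printed bins are days is an inference from identical cut-points in Section 8.2.1.1. It is strong, but it is not printed in the table. The cycle reading of onset further assumes that days are counted from first dose and that infusions are on schedule.

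The effect is confined to the categorical rows of one descriptive table for an event of special interest. The response rate, the stopping rules and the error rates are untouched.

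**What to change.** 1. Replace the categories in the Table 3.0033 note with the hour categories of Section 8.2.1.1, and print the unit.
2. State that IRR onset and duration are derived from start and stop date/times, not by the whole-day rule of Section 16.6.4, which cannot fill hour categories. Section 16.4.2 refers to adverse event times only if collected, so confirm that they are, and say how IRRs without a time are shown.
3. State the onset origin, for example the start of the infusion concerned. Two drugs are infused on the same day (Section 2.3), so say which infusion is meant.
4. Add an onset category above 24 hours, in both Section 8.2.1.1 and the table, for events that qualify by preferred term or start late after the infusion.

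The cost is one programming note, one derivation line and one added category. The fix itself asks for no new data, provided that event times are already collected.

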8.2.1.2. Corneal Events (GSK Scale)

After discussions with regulatory agencies, GSK developed a grading scale to capture both corneal examination findings and visual acuity changes in participants treated with belantamab mafodotin. This GSK scale differs from the CTCAE criteria for eye disorders which relies mainly on patient’s symptoms and patient’s ability to attend to ‘activities of daily living’ for grading of events.

Severity of belantamab mafodotin treatment related corneal events will also be graded using the GSK scale for corneal events and should be used for evaluation of DLT.

Summaries of the number and percentage of subjects with these events will be provided for each type of grade separately by visit. The time of onset and duration of first

occurrence of grade 2 or above events, and the event characteristics will be summarized similarly as the AESIs for belantamab mafodotin provided in Section 8.2.1.1.

In addition to the listing, the following outputs will be provided for corneal events graded using the GSK scale:

1. Overview for corneal event (GSK scale)
2. Summary of actions taken with study treatment (e.g. dose reduction/delay/study treatment withdrawn)

The details of the planned displays are provided in [Appendix 11: List of Data Displays](#).

8.2.1.3. Identified Risks: Neutropenia

Characteristics (e.g., number of occurrences, action taken, grade, etc.) of the important identified risk, neutropenia, will be summarized separately. The severity of neutropenia will be graded utilizing the NCI-CTCAE v.4.03 [[NCI](#), 2010].

A comprehensive list of MedDRA preferred terms for neutropenia based on clinical review will be used to identify each type of event similarly as the AESIs for belantamab mafodotin provided in Section 8.2.1.1. The details of the planned displays are provided in [Appendix 11: List of Data Displays](#).

Summaries of the number and percentage of subjects with these events will be provided for each type of events separately by preferred term and maximum grade. The time of onset and duration of first occurrence of each type of events in days, and the event characteristics will be summarized similarly as the AESI for belantamab mafodotin provided in Section 8.2.1.1.

8.2.2. Pembrolizumab

8.2.2.1. Overdose

For pembrolizumab, an overdose as defined in Section 6.10 of protocol that is not associated with clinical symptoms or abnormal laboratory results is an AESI.

A comprehensive list of MedDRA preferred terms for overdose based on clinical review will be used to identify each type of event similarly as the AESIs for belantamab mafodotin provided in Section 8.2.1.1. The details of the planned displays are provided in [Appendix 11: List of Data Displays](#).

8.3. Deaths and Serious Adverse Events

All deaths will be summarised based on the number and percentage of subjects. This summary will classify subjects by time of death relative to the last dose of medication (>30 days or ≤30 days) and primary cause of death (disease under study, SAE related to

study treatment, or other). A supportive listing will be generated to provide subject-specific details on subjects who died and have fatal SAEs and fatal serious irAEs.

All SAEs will be tabulated based on the number and percentage of subjects who experienced the event. Separate summaries will also be provided for study treatment-related SAEs. The summary Tables will be displayed in descending order of total incidence by SOC and PT.

A study treatment-related SAE is defined as an SAE for which the investigator classifies the relationship to study treatment as “Yes”. A worst-case scenario approach will be taken to handle missing data, i.e. the summary Table will include events with the relationship to study treatment as ‘Yes’ or missing.

SAEs are included in the listing of all adverse events and immune-related adverse events. Separate supportive listings with subject-level details will be generated for

- Non-Fatal SAEs.
- Non-Fatal serious irAEs

8.4. Adverse Events Leading to Discontinuation of Study Treatments and Other Significant Adverse Events

The following categories of AEs will be summarized for separately in descending order of total incidence by SOC and PT and separate supportive listings will be generated with subject level details for those subjects:

- AEs Leading to Permanent Discontinuation of Study Treatment (belantamab mafodotin and pembrolizumab)
- AEs Leading to Dose Interruptions (belantamab mafodotin and pembrolizumab)
- AEs Leadings to Dose Reductions (belantamab mafodotin)
- All Treatment-related Serious Adverse Events (belantamab mafodotin and pembrolizumab)

8.4.1. Immune-Related Adverse Events Leading to Discontinuation of Study Treatments and Other Significant Adverse Events

The following categories of irAEs will be summarized for separately in descending order of total incidence by SOC and PT and separate supportive listings will be generated with subject level details for those subjects:

- irAEs Leading to Dose Interruptions (Pembrolizumab)

